5. Nursing staff will compare AM and HS (before breakfast and at bedtime) POC glucometer reading to concomitant CGM reading to ensure readings remain accurate (within +/- 15% of each other). If CGM readings will fall outside this range, nursing will contact the research team for directions. The research team will recommend either to retest the accuracy of the sensor with POC glucometer, or to exchange the CGM sensor and then test the accuracy

The CGM will be set up with alarm limits of 85 for low glucose and 250 for high glucose. If these alarms are triggered, the nursing staff will take measures for these alarms as listed below. Treatment decisions will be made based on the POC glucometer reading as follows:

- For hypoglycemia alarm (BG<85mg/dl), POC glucometer will be used to confirm the glucose level. Measures will be taken to prevent or treat hypoglycemia.
 - If BG is 70-85mg/dl, patient will receive 15 gm of carbohydrates PO ASAP and blood glucose will be re-checked in 30 minutes.
 - If BG is <70, hypoglycemia protocol will be initiated. IV D50 pushes or IM glucagon will be used if patient is obtunded and unable to swallow. POC glucose will be re-checked in 15-30 minutes to ensure appropriate correction of hypoglycemia.
- For hyperglycemia (sustained BG>250) for more than 2 hours in a row, nursing staff will contact primary provider or inpatient endocrinology team for insulin dosing recommendations. POC glucose check will be obtained based on provider recommendations. Additional insulin will not be given between meals regardless of sensor reading unless otherwise recommended by attending physician or ARNP provider. Close attention will be given to avoid “insulin stacking phenomenon” and potential hypoglycemic events.

For patients receiving IV Insulin infusion:

Please note that during the entirety of the study while the patient is receiving IV insulin, the insulin infusion dose will only be adjusted using the POC BG readings. CGM data will only be used to monitor BG range and if BG is found to be outside of expected range, the POC glucose will be checked and insulin infusion will be adjusted based on the POC glucometer reading.

Adjustment Phase

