4. Once BG remains within range for 2 consecutive POC glucometer readings, POC glucose checks will be again decreased to every 2 hours

5. If the patient is transitioned from IV insulin infusion to SQ insulin, the nursing staff will notify the research staff and will proceed to the SQ insulin protocol above. The alarms will be adjusted as described in the SQ insulin protocol.

The CGM will be set up with alarm limits of **Low Glucose (<140 mg/dl)**, **Urgent Low Glucose (<70)** and **High Glucose (>180)**. If these alarms are triggered, the nursing staff will perform a STAT POC glucose check to confirm blood glucose (BG) level. Treatment decisions will be made based on the POC glucometer reading as follows:

- For hypoglycemia:
 - If POC BG is between 85-140 mg/dl, hold IV insulin infusion and re-check POC glucose in 30 minutes
 - If POC BG is between 70-84 mg/dl, hold IV insulin and ask patient to take 15gm of carbohydrates PO ASAP and recheck POC glucose level in 30 minutes
 - If POC BG is < 70, apply hypoglycemia protocol. Hold IV insulin. Give IV D50 or IM glucagon to obtunded patients. Give PO carbohydrates to alert, able to swallow patients. Repeat POC glucose level in 15 min. and 30 min.
 - Continue to check POC blood glucose every 1 hour until glucose remains in range (140-180 mg/dl) for 2 consecutive readings.
 - Once BG remains within range for 2 consecutive POC glucometer readings, POC glucose checks will be decreased to every 2 hours
- For hyperglycemia (BG>180):
 - Check glucose level using POC glucometer and adjust IV insulin infusion rate accordingly
 - Continue checking POC glucose every 1 hour until glucose remains in range (140-180 mg/dl) for 2 consecutive readings
 - Once BG remains within range for 2 consecutive POC glucometer readings, POC glucose checks will be decreased to every 2 hours

Methods (continued):

Treatment of the DM and associated complications, dosing of the insulin, change from PO to insulin treatment and back to PO medications during hospitalization or at discharge will be guided by the admitting team with as needed help from the inpatient Endocrinology Consultation Service.

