**Outcomes measured:**

CGM accuracy when compared with POC monitors.

CGM accuracy at detection of hypo or hyperglycemia episodes when compared with POC monitors.

Number of CGM alarms and the clinical result of these alarms: nurse notification, treatment of hypo or hyperglycemia episodes, treatment for rapid declining glucose alarms.

Number of POC glucometer checks in the “Adjustment Phase” and in “Utilization Phase” will be recorded.

Hospital outcomes (length of stay, mortality, readmission and mortality at 30 days)

Patient satisfaction with DM management and inpatient care overall.

Criteria for Discontinuation of Individual Participants:

Subjects can decide to discontinue entirely from the study at any time for any reason. This is documented as withdrawal of consent. Subjects can also be discontinued from the study or discontinued from the study treatment due to Investigator decision as detailed below.

1. Withdrawal of consent.
2. At the Investigator’s discretion in certain situations such as lack of compliance or serious adverse event. (A single severe hypoglycemic event resulting in seizure or LOC or DKA).
3. 2 or more hypoglycemic events based on CGM readings that do not correlate with standard finger-stick blood glucose monitor readings and decision to remove the sensor.
4. One DKA event or one episode of hyperglycemic, hyperosmolar nonketotic syndrome (HHNS).
5. Skin infection at the site of device insertion that occurs after placement of the device.
6. Skin irritation at the site of device insertion prompting the patient to request removal of the device.
7. Transfer of the patient to the ICU with intubation, shock, placement on ECMO (Extracorporeal membrane oxygenation) or deterioration of medical condition that in the judgment of the principal investigator carries an unacceptable risk for the participant.

Materials:

CGMs (G6 sensors, G6 transmitters and Phone readers) provided and purchased from DEXCOM . iPad tablets provided by Mayo Clinic IT Department.

DEXCOM G6 app software is preinstalled on phone readers.

DEXCOM Follow app will be installed on iPads present at nursing station.

Personnel:

Diabetes educators and Endocrinology APRN will provide support for nursing staff and perform the tasks listed above.

Subject Information

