The study will use data that have been collected under another IRB protocol. Include in the Methods section and enter the IRB number from which the research material will be obtained. *When appropriate, note when subjects have provided consent for future use of their data and/or specimens as described in this protocol.*

Enter one IRB number per line, add more lines as needed

Data Specimens Data & Specimens _____

Data Specimens Data & Specimens _____

Data Specimens Data & Specimens _____

Data Analysis

Power Statement:

This a pilot study to demonstrate feasibility of CGM use in COVID patients and to determine if a subsequent more extensive implementation and studying of this device will be warranted.

Data Analysis Plan:

Data will be described as percentages or means. Pearson χ^2 and Kruskal Wallis tests will be used to compare categorical and continuous variables respectively. Odds ratios, 95% confidence intervals and p-values will be reported for each model. All tests of significance will be 2-sided and the level of statistical significance will be set at p-value < 0.05 .

Mean Absolute Relative Differences will be calculated between matched pairs of POC monitors and the closest CGM reading (within 5 minutes of POC). Additionally, level of agreement between the two devices will be examined with Bland-Altman plots, with particular attention focused on detection agreement in range (70-180 g/dl). Poisson or negative binomial regression will be utilized to assess count variables such as number of alarms, nurse notification, and hypo or hyperglycemia events adjusting for patient characteristics. Finally, longitudinal analysis will be conducted to determine differences associated with medications, clinical parameters or diagnosis. Analysis will seek to define if there are any differences between CGM and POC measurement based on these changes.

Endpoints

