**Primary:**

CGM accuracy - mean absolute relative difference (MARD)

The frequency of POC glucometer use in Adjustment and Utilization phase

Secondary:

- CGM accuracy at detection of hypo or hyperglycemia episodes when compared with POC monitors. (MARD for readings <70g/dl, >180g/dl, >250g/dl)
- CGM accuracy for detecting time in range (70-180 g/dl MARD).
- Number of CGM alarms and the clinical result of these alarms: nurse notification, treatment of hypo or hyperglycemia episodes, treatment for rapid declining glucose alarms.
- Time in therapeutic range for glucose as measured by CGM and POC glucose monitor.
- Detection of medications, clinical parameters or diagnoses that would interfere with CGM reading.
- Effect of CGM use on length of hospital stay.

Clinical safety measures:

- Patients with severe hypoglycemia episodes (POC glucose check below 50 mg/dl).
- Patients with DKA or HHS diagnoses after admission and enrollment in the study.
- Number of sensors with failure.
- Number of sensors removed for procedure.
- Number of sensor related skin reaction (contact dermatitis, infection)

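### The severe-hypoglycemia safety measure counts only POC values below 50 mg/dl, so a hypoglycemic seizure or loss of consciousness that led to discontinuation could go unreported as severe

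*Combined protocol and SAP*

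**What the plan says.** Two sections of the combined protocol and SAP speak of severe hypoglycemia.

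- **Endpoints, Clinical safety measures.** The first item is "Patients with severe hypoglycemia episodes (POC glucose check below 50 mg/dl"). The criterion is a glucose value alone. The second item is "Patients with DKA or HHS diagnoses after admission and enrollment in the study". The remaining items concern sensor failure, sensor removal for procedures and skin reactions.
- **Criteria for Discontinuation of Individual Participants, item 2.** A participant may be discontinued "At the Investigator’s discretion in certain situations such as lack of compliance or serious adverse event". The example in parentheses is "A single severe hypoglycemic event resulting in seizure or LOC or DKA". The criterion here is a clinical consequence, and no glucose value is attached.

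Three other places bear on the point. In the subcutaneous protocol, "If BG is <70, hypoglycemia protocol will be initiated", and the IV protocol uses the same level. The Data Analysis Plan models counts of "number of alarms, nurse notification, and hypo or hyperglycemia events adjusting for patient characteristics" by Poisson or negative binomial regression. The secondary endpoints include CGM alarms and the treatment that followed them. Neither the model nor the alarm endpoint grades hypoglycemia by severity.

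**The concern.** The same adjective is tied to a clinical outcome in one section and to a meter reading in the other, and the plan does not connect them. A participant could have a hypoglycemic seizure and be discontinued for it. If no POC value below 50 mg/dl was recorded, the safety table would still show that participant as free of severe hypoglycemia.

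This matters because the hypothesis is that POC checks can be made less often without loss of safety, and the pilot is meant to inform whether wider use is warranted. Severe hypoglycemia is the first safety measure listed. A report of no severe hypoglycemia, in a study where a participant was withdrawn after a hypoglycemic seizure, would mislead on the question that the measure is there to answer.

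**Working it through.** The plan states no event rate, sample-size derivation or safety threshold for this measure, so there is no figure to reproduce. The check is a comparison of the text, followed by an illustration of scale.

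**Step 1. Cross-classify a hypoglycemic event under the two sections as written.**

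| Event | Within the item 2 description? | In the severe-hypoglycemia measure? |
|---|---|---|
| Seizure or LOC, POC below 50 recorded | Yes | Yes |
| Seizure or LOC, no POC below 50 recorded | Yes, unless severe is taken to mean POC below 50 | No |
| No seizure or LOC, POC below 50 recorded | No | Yes |
| No seizure or LOC, no POC below 50 recorded | No | No |

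The second row is the gap. It includes POC values of 50 to 69 mg/dl, which both insulin protocols treat as hypoglycemia because their hypoglycemia step starts below 70. The third row is not a fault: a safety count may be wider than a stopping criterion.

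**Step 2. Look for another safety measure that would pick up the second row.**

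- DKA and the hyperosmolar state (discontinuation items 2 and 4) have a counterpart in the DKA or HHS measure.
- Skin infection and irritation (items 5 and 6) have a counterpart in the skin-reaction measure.
- Hypoglycemic seizure or LOC (item 2) has no counterpart unless a POC value below 50 was also recorded.
- The hypoglycemia event count and the alarm-treatment endpoint could include the episode, but without marking it as severe.

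**Step 3. Scale, for illustration.** Inputs: n = 20 (Subject Information, target accrual) and two-sided exact Clopper-Pearson 95% limits. The number of affected patients, one, is an assumption.

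- One patient: 1/20 = 5.0%.
- x = 0: upper limit = 1 − 0.025^(1/20) = 0.1684, giving 0% to 16.8%.
- x = 1: lower limit = 1 − 0.975^(1/20) = 0.0013. The upper limit solves (1 − p)^20 + 20p(1 − p)^19 = 0.025, so p = 0.2487. The interval is 0.1% to 24.9%.

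Leaving out one patient lowers the estimate by 5.0 percentage points and the upper limit by 24.9 − 16.8 = 8.1 points.

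**The case against.** **The discontinuation item is not a definition.** It can be read as a severe event, in the sense of POC below 50, that also produces seizure or LOC. On that reading every such event is already counted. This stands as a possible reading: item 2 describes an event and does not define one. But nothing in the documents makes the link, and one sentence would settle it.

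**A stopping criterion and a safety endpoint need not match.** This is right. It would be too strong to infer that the two must share one definition, or that item 2 should be rewritten. Item 2 is also discretionary, so discontinuation is not automatic. Neither fact explains why seizure or LOC from hypoglycemia is missing from the safety measures when other harms in the same list have a counterpart there.

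**Obtundation.** A reader might infer that a patient who is obtunded at a POC of 50 to 69 also meets item 2, since the subcutaneous protocol says "IV D50 pushes or IM glucagon will be used if patient is obtunded and unable to swallow" and the IV protocol has "Give IV D50 or IM glucagon to obtunded patients". The documents do not support this. Item 2 names seizure, LOC or DKA. Obtundation appears only as a guide to the route of treatment and is neither a severity grade nor a ground for discontinuation.

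**Treatment before any POC value.** A reader might also suppose that patients would routinely be treated before a glucose value is taken. The written alarm response runs the other way: a low alarm calls for a POC check, and treatment follows that reading. An unmeasured event would have to arise outside that pathway or depart from it.

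**The event would not vanish.** It would be known to the investigator if it led to discontinuation, and it might enter the general counts. That limits the exposure to how the event is labelled in the safety report.

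**The interval figures are generic.** They would be the same for any yes/no item in 20 patients, and the plan ties no decision to this proportion. That is correct, and they serve only as illustration.

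**Conclusion.** The point holds as a reporting gap. As written, the safety measure can omit a hypoglycemic seizure or LOC for which no POC value below 50 mg/dl was recorded, although the same event could be a ground for discontinuation. It is not shown that such an event is likely, that it would go wholly unrecorded, or that either clinical criterion is wrong.

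The conclusion rests on two readings of the text: that item 2 is not silently limited to POC below 50, and that no adverse-event section outside the available text captures these events by severity. The first is open, which is why the claim is that an event may go uncounted and not that it will.

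In size, each omitted patient is 5 percentage points of 20. The shift from 24.9% to 16.8% in the upper limit assumes full accrual and exactly one affected patient. The qualitative consequence matters more: a reported zero for severe hypoglycemia that does not mean what a reader would take it to mean.

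**What to change.** Reconcile the discontinuation criteria and the clinical safety measures on reporting, so that every hypoglycemic event with seizure or LOC is also a reported safety outcome. In the safety measures, report by patient:

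1. patients with a POC value below 50 mg/dl, as now;
2. patients with a hypoglycemic event accompanied by seizure or LOC, whatever the POC value;
3. patients with either, each counted once.

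Give each count with its denominator and an exact 95% interval.

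The discontinuation rule stays as it is, and any clinical threshold remains for the sponsor to set.

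The cost is about one line of endpoint wording. The documents do not say that seizure or LOC is charted in a set place, so the team should confirm where it will be recorded. The safety figure may become slightly less favourable, but it would then support a statement on whether POC checks were reduced safely.

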Currently, the hospital standard of care for glucose monitoring in diabetic patients is POC capillary blood glucose measurement performed usually before meals and at bedtime. This approach however only provides limited glucose measurements throughout the day and fails to detect nocturnal or asymptomatic hypoglycemia or hyperglycemia episodes, all of which are common insulin therapy complications. Continuous Glucose Monitors (CGM), a newly introduced technology, represent an alternative to this standard of care, with the potential to assist making personalized therapy decisions. CGMs measure and record levels of subcutaneous interstitial glucose every 5 minutes. The subcutaneous glucose measured by most recent CGMs closely mirror the capillary blood glucose levels. This continuous monitoring allows for better assessment of nocturnal or asymptomatic hypoglycemia or hyperglycemia, and shows glycemic patterns following treatment interventions. This monitoring allows for timely interventions, and was shown to reduce hyperglycemia and hypoglycemia episodes. Recent studies have demonstrated improved glycemic control in insulin-treated DM patients using

CGM in outpatient setting. FDA has approved these devices in outpatient setting for glucose monitoring and for dosing of insulin injection even without capillary blood glucose confirmation. In the outpatient setting these devices have become standard of care for both type 1 and type 2 diabetes management. Their use in inpatient setting is limited, and at this time it is not FDA approved. Concerns for reading accuracy in case of rapidly fluctuating clinical parameters, hypoxemia, tissue hypoperfusion and IV medications use have prevented the approval of these devices in inpatient setting. Still, when evaluated in hospitalized patients, small studies have found that CGMs are accurate and they can detect more episodes of hypo and hyperglycemia than POC glucometers, especially between meals and at night time.

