During the first 24 hours, sensor accuracy will be assessed. Patients will continue to have their blood glucose checked with POC glucometer concomitant with CGM use. CGM readings will be recorded in chart at the same time as POC glucometer reading is obtained. The glucometer readings and CGM data at the time of glucometer readings will be compared by nursing staff. The CGM readings should not be either 15% higher or 15% lower than the corresponding POC glucometer reading. Should this CGM reading fall outside this range, a second reading will be done within 30 minutes and readings will be compared to reassess accuracy. After the patient has had sensor in place for 24 hours and at least 4 POC glucometer glucose checks have been recorded and compared against CGM values and found to fall within the above range, the research team will be notified to determine if the frequency of POC checks can be safely decreased based on CGM accuracy.

If 2 or more consecutive CGM readings do not correlate with POC glucometer values, the research team will be notified. The research team will evaluate the data and decide if the sensor should be replaced and another 24-hour cycle of adjustment phase re-initiated, or if patient participation should be terminated. Only POC glucometer readings will be used to make decision about insulin dosing and administration during this phase. When charting insulin

administration, nursing staff will manually enter the CGM readings obtained at the time of insulin administration into the chart under the “comments” on the MAR screen.

If 4 comparison points – CGM readings and POC glucometer reading – are deemed accurate (within +/- 15% of each other for all 4 readings), then patient will enter the “Utilization Phase”.

Utilization Phase

During this phase, once the research team has confirmed CGM accuracy, POC glucometer AND CGM readings will be used to make decisions about insulin dosing and administration. The use of POC glucometer will be decreased as follows:

1. POC glucometer checks will be reduced from 4 times per day (qAC and QHS) to twice per day before breakfast and at bedtime (qAM and qHS)
2. Subcutaneous insulin dose for breakfast and bedtime will be determined based on POC readings
3. Subcutaneous insulin dose for lunch and dinner will be determined based on CGM readings
4. Nursing staff will continue to record CGM readings at the time of every insulin administration in the chart under the “comments” section on the MAR

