In the “Adjustment Phase”, during the first 12 hours, sensor accuracy will be assessed. Patients will continue to have their blood glucose (BG) checked with POC glucometer concomitant with CGM use. Nursing staff will check POC BG every 1 hour for the first 12 hours (as per established IV insulin infusion protocol). CGM readings will be recorded in chart at the same time as POC glucometer reading is obtained. These readings will be entered by nursing staff under the “comments” section of the MAR screen. The glucometer readings and CGM data at the time of glucometer readings will be compared by nursing staff. The CGM readings should not be either 15% higher or 15% lower than the corresponding POC glucometer reading. Should this CGM reading fall outside this range, a second reading will be done within 30 minutes and readings will be compared to reassess accuracy. After the patient has had sensor in place for 12 hours and at least 12 POC glucometer glucose checks have been recorded and compared against CGM values, the research team will be notified to determine if the frequency of POC checks can be safely decreased based on CGM accuracy.

If 12 comparison points – CGM readings and POC glucometer reading – are deemed accurate (within +/- 15% of each other for all 12 readings), then patient will enter the “Utilization Phase”.

If 2 or more consecutive CGM readings do not correlate with POC glucometer values, the research team will be notified. The research team will evaluate the data and decide if the sensor should be replaced and another 12-hour cycle of adjustment phase re-initiated or if patient participation should be terminated.

Utilization Phase

Once CGM accuracy has been established in the “Adjustment Phase” above, the frequency of POC glucose checks will be reduced as follows:

1. POC glucometer checks will be reduced to every 2 hours
2. CGM readings will continue to be recorded hourly by nursing staff.
 - a. If CGM glucose remains in range (140-180 mg/dl), the same insulin infusion rate will be continued.
 - b. If CGM glucose is out of range (<140 or >180) then nursing staff will resume POC glucose check every 1 hour. Insulin infusion will be adjusted as needed per IV insulin infusion protocol using the POC glucometer reading **only**.
3. If IV insulin infusion dose is adjusted, nursing staff will resume POC glucometer checks every 1 hour until the POC glucose remains in range for 2 consecutive readings

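### Severe hypoglycemia is counted only from POC values below 50 mg/dl, and in the Utilization Phase most unscheduled POC checks are prompted by the CGM under test, so the count is not an independent safety check

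*Combined protocol and SAP*

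**What the plan says.** Endpoints, under Clinical safety measures, lists five items. The first is "Patients with severe hypoglycemia episodes (POC glucose check below 50 mg/dl". It is a count of patients, with no CGM, laboratory, symptom or treatment component and no exposure denominator.

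The Methods change how often POC glucose is measured:

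- **Subcutaneous insulin, Utilization Phase:** "POC glucometer checks will be reduced from 4 times per day (qAC and QHS) to twice per day before breakfast and at bedtime". At the two times where the scheduled check is dropped, "Subcutaneous insulin dose for lunch and dinner will be determined based on CGM readings".
- **IV insulin:** in the Adjustment Phase, "Nursing staff will check POC BG every 1 hour for the first 12 hours"; in the Utilization Phase, "POC glucometer checks will be reduced to every 2 hours". The reduction is conditional: "If CGM glucose is out of range (<140 or >180) then nursing staff will resume POC glucose check every 1 hour".

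The CGM also prompts POC checks. For subcutaneous insulin, "The CGM will be set up with alarm limits of 85 for low glucose and 250 for high glucose", and a low alarm is to be confirmed by POC. For IV insulin, CGM readings below 140, below 70 or above 180 mg/dl call for an immediate POC check.

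The Background says that usual POC monitoring "fails to detect nocturnal or asymptomatic hypoglycemia". The hypothesis under Research Question and Aims is that, if the CGM proves accurate, POC frequency can be lowered safely.

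**The concern.** The measure rests on the instrument whose use the study reduces. Once scheduled checks are halved, a severe low enters the count mainly because the CGM raised an alarm and a nurse answered it with a POC test. If the CGM fails to show the low, no extra POC test is prompted, so the failure that matters most for safety also removes the evidence of it. In patients on subcutaneous insulin, the two checks removed are those where the dose is then set from the CGM.

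A low or zero count in the Utilization Phase could therefore be read as evidence that fewer POC checks are safe, when it partly reflects how well the CGM alarms worked. The way events are found also differs between phases, so the counts are not on the same footing.

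**Working it through.** The plan gives no event rate, power calculation or capture figure to reproduce. The check has four steps.

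**1. Scheduled checks.** Subcutaneous: 4 to 2 per day, 2/4 = 50%. IV: 24 to 12 per day, 12/24 = 50%.

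**2. CGM error needed to escape an alarm at a true 50 mg/dl.** Formula: alarm limit / 50 − 1.

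- Subcutaneous low alarm: 85/50 − 1 = +70%.
- IV low alarm: 140/50 − 1 = +180%.
- IV urgent low alarm: 70/50 − 1 = +40%.

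A sensor within the protocol's 15% tolerance would read at most 50 × 1.15 = 57.5 mg/dl and would alarm. Escape needs gross sensor error. However, the subcutaneous accuracy gate (four pairs within 15%) does not require any pair in the low range.

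**3. Chance that a low receives a POC check.** Let p = min(1, checks per day × duration in hours / 24), and let s be the chance that the alarm leads to a POC check during the low. Then capture = 1 − (1 − s)(1 − p). Duration and s are not in the documents. I assume durations of 0.25 to 2 hours and s from 0 to 0.95, random timing, and independence of alarm-prompted and scheduled checks.

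It matters whether alarm-prompted checks also apply in the Adjustment Phase. The Methods have alarm limits set at set-up, but the subcutaneous response rules stand under the Utilization Phase. Both cases are shown:

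- Alarms in both phases: loss = (1 − s)(p_adj − p_util).
- Alarms only in Utilization: capture is higher there once s exceeds 1 − (1 − p_adj)/(1 − p_util).

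| Protocol, duration | p_adj | p_util | Loss in points at s = 0 / 0.80 / 0.95 | Break-even s |
|---|---|---|---|---|
| SQ, 0.25 h | 4.2% | 2.1% | 2.1 / 0.4 / 0.1 | 2.1% |
| SQ, 0.5 h | 8.3% | 4.2% | 4.2 / 0.8 / 0.2 | 4.3% |
| SQ, 1 h | 16.7% | 8.3% | 8.3 / 1.7 / 0.4 | 9.1% |
| SQ, 2 h | 33.3% | 16.7% | 16.7 / 3.3 / 0.8 | 20.0% |
| IV, 0.25 h | 25.0% | 12.5% | 12.5 / 2.5 / 0.6 | 14.3% |
| IV, 0.5 h | 50.0% | 25.0% | 25.0 / 5.0 / 1.25 | 33.3% |
| IV, 1 h | 100% | 50.0% | 50.0 / 10.0 / 2.5 | Utilization never better |
| IV, 2 h | 100% | 100% | 0 / 0 / 0 | not applicable |

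The IV losses are upper bounds, because hourly POC resumes when the CGM leaves 140–180 mg/dl or the infusion is changed.

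For a one-hour low on subcutaneous insulin in Utilization, scheduled checks alone capture 8.3%. With s = 0.80, capture is 1 − 0.20 × 0.917 = 81.7%. Under that assumption, most capture comes through the CGM alarm.

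**4. Losses that need no sensor error.**

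- In the subcutaneous protocol, a POC result of 70–85 mg/dl after an alarm leads to a recheck 30 minutes later. A fall below 50 mg/dl and recovery in that interval could show on the CGM, which transmits every 5 minutes, but would not enter the count.
- The transmitter may be temporarily removed for tests, a new sensor shows nothing for 2 hours, and sensor failures are expected enough to be a listed measure. Without a signal there is no alarm-prompted check.

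**The case against.** The strongest reply is that the protocol replaces scheduled checks with alarm-prompted ones, so halving the schedule need not hide events. This stands. A reader might infer that severe lows become less visible in the Utilization Phase, or that fewer events there would simply mean fewer looks. The documents do not support that as a general statement: step 3 gives a loss in one case and a gain in the other, and the text does not settle which applies.

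Two further inferences fail. The measure is not named as the main safety measure; it is one of five unranked items. No between-phase comparison of it is planned: only POC frequency is specified by phase, and the count regression in the Data Analysis Plan names patient characteristics, not phase.

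It is also fair to say that POC is the comparator and a defensible way to confirm an event. Some related information is collected elsewhere: alarms and their results, treatment of low-glucose episodes, CGM time in range, and hypoglycemia with seizure or loss of consciousness among the discontinuation criteria. A later alarm or the bedtime POC check can still record a prolonged low. None of this makes the count independent of the CGM, and none of the other items is a count of severe lows from another source.

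**Conclusion.** The concern holds in limited form. In the Utilization Phase, capture of POC values below 50 mg/dl depends largely on the CGM alarm and the response to it. The count is therefore not an independent check on CGM failure, and ascertainment differs between phases.

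If alarms run in both phases and 80% lead to a check, the loss from halving the schedule is 0.4 to 3.3 points for subcutaneous insulin and at most 10 points for IV insulin, over the assumed durations. If alarm-prompted checks begin only in Utilization, subcutaneous capture for a one-hour low is higher there once s exceeds 9.1%. Whether visibility rises or falls overall cannot be determined from the documents.

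The figures rest on assumed durations, alarm response and random timing. With 20 patients any count will be imprecise: zero events still leaves a one-sided 95% upper limit of 1 − 0.05^(1/20) = 13.9% of patients. This is a worthwhile reporting improvement, not a defect that invalidates the study.

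**What to change.** Change the analysis text only:

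1. Keep the count of patients with POC below 50 mg/dl as the confirmed measure.
2. Beside it, report episodes with CGM below 50 mg/dl and with laboratory glucose below 50 mg/dl, by source and by whether POC confirmed them. State in advance what makes a CGM episode and what time window counts as confirmation.
3. Give patient-days of observation in each phase, and present the results descriptively, without a test between phases.
4. List separately hypoglycemia events with seizure or loss of consciousness, and charted IV dextrose or glucagon. Do not class these as severe by glucose value: the hypoglycemia protocol starts below 70 mg/dl, so many treated episodes may lie between 50 and 69.

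The cost is small. CGM data, laboratory values and administered medications are already to be collected. Retention of the full CGM trace is implied by the time-in-range endpoint but not stated, and should be confirmed.

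There are two limits. Some CGM-only lows will be false, which is why the source is shown. Adding CGM values also cannot recover a low that the CGM reads falsely high; only the laboratory, symptom and treatment records can. No change to doses, alarm limits or check frequency is proposed.
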